- Serious adverse device events and device deficiencies will be collected during each subject follow-up. Confirmation of absence of USADE during “In-Clinic LVAT” tests will be evaluated by analyzing all SAEs and device deficiencies collected at each follow-up.
- The focus of the “In-clinic LVAT” deficiencies will include:
 - o Assessment of pacing threshold underestimation: comparison to manual LV threshold value will be performed by comparing manual and automatic LV threshold values at each follow-up. An underestimated LV threshold value of “In-Clinic LVAT” feature is defined as a value result more than 2 steps below the LV threshold measured manually. For all the eligible complete LV Vector Tests collected, only manual LV threshold test performed in the same conditions and reported in the electronic Case Report Form (eCRF) will be retained. Only one LV Vector Test per LV pacing vector per subject will be analyzed. In case several LV Vector Tests are eligible with the same LV pacing vector, for the same subject, on the same follow-up, only the last one will be considered.
 - o Confirmation of absence of unexpected function operations by analyzing EGM and ECG performed during “In-Clinic LVAT” test at each follow-up. Any unexpected function operation will be reported.

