6.1. TREATMENT AND EVALUATION

6.1.1. *Inclusion follow-up*

Subjects must be informed about the investigation and the potential benefits and risks of the study prior to enrollment. Only those subjects who voluntarily provide written consent to participate will be eligible for enrollment.

The following procedures must be conducted before inclusion of the subject in the study:

- Evaluate subject eligibility based on the inclusion and exclusion criteria
- Obtain written informed consent
- Source data that demonstrate conformance with inclusion criteria should be retained at the investigational site

The following procedures must be conducted in order to include the subject in the study:

- Report implant information
- Report subject's medical history
- Report subject's clinical examination including current vital signs and NYHA classification
- Report subject's current concomitant medications (based on the EDC questions)

6.1.2. *M0 follow-up*

- Perform a complete interrogation of the device with the appropriate clinical programmer
- Print report file
- Measure P-R, A-R and V-V inter ventricular conduction durations on the EGM
- Launch manual LV threshold tests on:
 - 5 common LV vectors to IS1 and IS4 for all subjects,
 - 4 dedicated IS4 LV vectors for subject implanted with IS4 LV lead (LV2-LV4, LV3-LV4, LV3-LV2, LVtip1-LV4).

Manual tests should be performed prior to automatic test to limit bias.

Optional manual threshold tests on additional LV pacing vectors could be performed under physician discretion.

- ECG record:
 - Spontaneous rhythm,
 - Paced rhythm during “In-Clinic LVAT” test in DDD A-test for 30 seconds recording corresponding to 10 seconds before launching test and 20 seconds during the test.
- Launch “In-Clinic LVAT” test on all LV pacing vectors in following pacing configuration:
 - DDD A-test
 - DDD P-test
 - VVI
- Perform right ventricular pacing recordings data collection using RF telemetry to allow collection of multiple EGM:
 - RV A-test

- RV P-test
- Retrieve subject technical data analysis files
- Report Adverse Events and Serious Adverse Events occurred during the testing procedure if any
- Report Device Deficiencies if any

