6.1.3. M1 follow-up

- Perform a complete interrogation of the device with the appropriate clinical programmer
- Print report file
- Measure P-R, A-R and V-V inter ventricular conduction durations on the EGM
- Launch manual LV threshold tests on:
 - 5 common LV vectors to IS1 and IS4 for all subjects,
 - 4 dedicated IS4 LV pacing vectors for subject implanted with IS4 LV lead (LV3-can, LV3-RVring, LV3-RVcoil, LV4-RVcoil).

Manual tests should be performed prior to automatic test to limit bias.

Optional manual threshold tests on additional LV pacing vectors could be performed under physician discretion.

- ECG record:
 - Spontaneous rhythm,
 - Paced rhythm during “In-Clinic LVAT” in DDD A-test for 30 seconds recording corresponding to 10 seconds before launching test and 20 seconds during the test.
- Launch “In-Clinic LVAT” test on all LV pacing vectors in following pacing configuration:
 - DDD A-test
 - DDD P-test
 - VVI
- Perform right ventricular pacing recordings data collection using RF telemetry to allow collection of multiple EGM:
 - RV A-test
 - RV P-test
- Retrieve subject technical data analysis files
- Report Adverse Events and Serious Adverse Events occurred during the testing procedure if any
- Report Device Deficiencies if any
- Report Serious Cardiovascular Adverse Event occurred since last follow-up if any

6.1.4. *Unscheduled follow-ups*

If the subject comes in due to a serious cardiovascular adverse event, re-intervention, or if the subject’s device is interrogated for any reason outside of regular follow-up, the routine follow-up procedure should be performed when possible.

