10.2. PRINCIPAL INVESTIGATOR'S RESPONSIBILITIES IN ADVERSE EVENT REPORTING

The responsibilities of the principal investigator include the following:

- The Principal Investigator is required to report the following adverse events to the Sponsor:
- Unanticipated Serious Adverse Device Effects should be reported to the Sponsor within 24 hours of awareness of the event by notifying the Sponsor Clinical Project Manager and by entering the information in the EDC. These events require urgent investigation by the Sponsor and reporting to regulatory authorities, as applicable.
- All adverse events (serious and non-serious) during the testing procedure should be reported. However, conditions that occur due to direct physiologic effects of testing (e.g. PNS, palpitations, and discomfort) are not considered adverse events.
- Serious cardiovascular and access site adverse events from inclusion (signing date of informed consent) to termination should be reported as soon as possible but no later than 3 calendar days upon awareness. The Principal Investigator should enter all available information in the “AE section” of the EDC system. Cardiovascular events refer to those that are classified under cardiac disorders, bleeding disorders, cerebrovascular, and peripheral vascular as defined in the trial-specific AE classifications (Appendix B).
- Device deficiencies should be reported within 5 calendar days of awareness. Deficiencies of the Sponsor study device should be reported in the Device Deficiencies section in EDC. The Principal Investigator must return the device, if possible, to the Sponsor. Deficiencies of the non-Sponsor study device should be reported following the commercial reporting procedure for that device.

Timelines and Communication Methods for Reporting Adverse Events

Study Period	Event Classification	Communication Method	Communication Timeline
During initial testing procedure	All adverse events e.g. procedural complications (serious and non-serious), excluding direct physiologic effects of testing	Complete AE eCRF page with all available information.	Within 3 calendar days of first becoming aware of the event
Throughout study duration	All Serious cardiovascular and access site Adverse Events	Complete AE eCRF page with all available information.	Within 3 calendar days of first becoming aware of the event

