Throughout study duration	All deaths	Complete AE eCRF page with all available information. Provide all relevant source documentation (unidentified) for reported event	Within 1 business day of first becoming aware of the event.
Throughout study duration	Unanticipated (Serious) Adverse Device Effect	Complete AE eCRF page with all available information. Provide all relevant source documentation (unidentified) for reported event	Within 1 business day of first becoming aware of the event. Reporting of any updated information required through the end of the study
Throughout study duration	Device Deficiencies (including but not limited to failures, malfunctions, and product nonconformities) with or without associated adverse events	Complete Device Deficiency eCRF with all available new and updated information	Within 5 days first becoming aware of the event and as per local/regional regulations Reporting required through the end of the study

- The Principal Investigator should perform the following assessments for each reported serious adverse event:
 - Identify the clinical event (Diagnosis or symptoms),
 - Seriousness of the event,
 - Relationship of the event to the device and/or procedure.
- The Principal Investigator should provide all the information needed to complete the AE electronic CRF.

- The Principal Investigator is responsible for informing the Ethics Committee, and regulatory authorities of serious adverse events as required by local/regional regulations.
- The Principal Investigator is expected to assist in clinical review and supply the Sponsor with relevant source documents and results of ancillary procedures required in the CIP.

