10.3. SPONSOR REPORTING RESPONSIBILITIES

The Sponsor is responsible for reporting serious adverse event information to all participating investigators, ECs and regulatory authorities, as applicable following local regulations. USADE investigation results will be reported to the competent authorities all ECs and all participating investigators within 10 working days of the Sponsor's first notice of the effect. The Sponsor will also notify the competent authorities, all ECs, and all participating investigators of any EC withdrawal of approval within 5 working days of receipt of the approval withdrawal.

If the Sponsor determines an USADE to be an unreasonable risk to subjects, all parts of the investigation presenting that risk will be terminated or suspended as soon as possible, no later than 5 working days after said termination and no later than 15 working days after the Sponsor' first notice of the USADE. All SAEs must be reported to EC following the EC's safety reporting guidelines. The suspended study may not resume until the study has received both EC and FDA approval.

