11. SECONDARY SAFETY ANALYSES

11.1. ASSESSMENT OF THE DEVICE CHARACTERISTICS IN TERMS OF SAFETY AND DEVICE DEFICIENCY

- A. Serious adverse device events and device deficiencies will be collected during each subject visit. Confirmation of absence of USADE during “In-Clinic LVAT” tests will be evaluated by analyzing all SAEs and device deficiencies (DD) collected at each visit.

This secondary endpoint will be based on IP.

- B. Algorithm characteristic: Underestimated Assessments

Assessment of LV pacing threshold underestimation: comparison to manual LV threshold value will be performed by comparing manual and automatic LV threshold values at each visit. An underestimated LV threshold value of “In-Clinic LVAT” feature is defined as a value result more than 2 steps below the LV threshold measured manually (meaning -0.5V if threshold<2.5V, else -1V as measured) . Please see table 6.

LEVEA – Statistical Analysis Plan

Number and percentages of “underestimated” assessments will be presented along with the exact 95% CI (Clopper & Pearson, 1934) by M0 and M1 visit. Only subjects with non-missing manual data will be considered.

The reasons for LV pacing threshold underestimation at M0 visit will be presented as table and listing. The missing reasons (if any) for underestimation will be presented as “Not available”. For the table, the number and percentages of the reasons will be presented with the denominator of the percentages based on the total number of LV pacing threshold underestimated.

Total number of attempted, completed,, Underestimated LV vector tests will be presented by LV vector for each LV pacing configuration by visit.

For the LV tests performed for patients with either IS1 and IS4 leads (six LV vectors common to IS1 and IS4) , the percentage for the number of LV vector tests “attempted”, will be calculated based on the number of patients implanted with either IS1 and IS4 leads.

For the LV tests performed for patients with IS4 leads (eight LV vectors pertaining only to IS4), the percentage for the number of LV vector tests “attempted”, will be calculated based on the number of patients implanted with IS4 lead.

For number of LV vector tests “completed”, the percentage will be calculated based on the number of LV vector tests attempted.

For number of LV vector tests “Underestimated”, the percentage calculated based on number of Complete LV vector tests .

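### Outside testing, protocol 10.2 collects a narrower set of events than protocol 4.1.3 e, protocol 10.3 and the SAP 14.2 tables assume, and no scheduled visit asks about the time from inclusion to M0

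*Protocol*

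**What the plan says.** **What is collected.** During testing, protocol 10.2 makes every AE reportable, serious or not, apart from direct physiological effects of the test. For the rest of the study its first category is: "Serious cardiovascular and access site adverse events from inclusion (signing date of informed consent) to termination should be reported as soon as possible". The text and timeline table of 10.2 add deaths, USADEs, and device deficiencies whether or not an AE accompanies them. SAP 14.1 repeats this list.

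**What is assumed elsewhere.** Protocol 4.1.3 e states: "Serious adverse device events and device deficiencies will be collected during each subject follow-up". Absence of USADE during the automatic tests "will be evaluated by analyzing all SAEs and device deficiencies collected at each follow-up"; SAP 11.1 A says the same of each visit. Protocol 10.3 states: "All SAEs must be reported to EC". SAP 14.2 plans overall rows for any AEs, any ADEs, SAEs, expected and unexpected SADEs, and SAEs related to neither device nor procedure.

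**What the visits ask.** The M0 list has "Report Adverse Events and Serious Adverse Events occurred during the testing procedure if any". The M1 list repeats that item and adds "Report Serious Cardiovascular Adverse Event occurred since last follow-up if any". The synopsis schedule matches.

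**Causality.** Under 10.2 the investigator "should perform the following assessments for each reported serious adverse event", relationship to device or procedure being one of them. SAP 14.1 and 14.2 tabulate relationship for AEs in general.

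**The concern.** Three parts of the plan use unrestricted terms (all SAEs, serious adverse device events, ADEs), while the section that tells sites what to report uses a restricted list. A site that follows 10.2 exactly will send the sponsor less than 10.3 and 4.1.3 e describe. A reader of the final report will see rows headed SAEs or Any ADEs with nothing to show that some classes were never requested outside testing.

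The visit checklists add a second gap. The duty in 10.2 runs from consent, but the M0 checklist does not ask what has happened since inclusion, and the M1 question looks back only to the previous follow-up. For IS1 subjects, who are included within 5 days of implant, the unprompted interval falls early after the procedure.

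At stake is whether the overall safety tables are complete and correctly labelled. The primary endpoint is not affected.

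**Working it through.** This is a comparison of passages; the plan gives no figure to reproduce.

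**Step 1. Event classes outside testing, against protocol 10.2.**

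| Event class outside testing | Required by 10.2? | Where a wider scope is assumed |
|---|---|---|
| Serious cardiovascular or access-site AE | Yes, from consent | none |
| Death | Yes | none |
| USADE | Yes | none |
| Device deficiency, with or without an AE | Yes | none |
| Non-fatal SAE that is neither cardiovascular nor access-site, not a USADE, and not tied to a device deficiency | No | Protocol 10.3; SAP 14.2 SAE rows, including those for SAEs other than death and SAEs with no device or procedure relationship |
| Anticipated SADE of that same kind | No | Protocol 4.1.3 e; SAP 14.2 expected SADE row |
| Non-serious AE or ADE not tied to a device deficiency | No | SAP 14.2 rows for any AEs and any ADEs |

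The last three rows are the gap. The protocol glossary separates anticipated from unanticipated SADEs, and 10.2 asks only for the unanticipated ones throughout the study. The expected SADE row can therefore be complete only for testing events, for cardiovascular or access-site events and deaths, and for events that arrive with a deficiency.

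**Step 2. What each visit asks.**

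- Inclusion (6.1.1): no adverse event item.
- M0 (6.1.2 and synopsis): events during testing, and device deficiencies.
- M1 (6.1.3 and synopsis): events during testing, device deficiencies, and serious cardiovascular events since the last follow-up, which is M0 or later. Access-site events are not named.
- Unscheduled (synopsis): serious cardiovascular events and device deficiencies, if such a visit takes place.

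No scheduled visit looks back from M0 to inclusion. M0 may be up to 15 days after inclusion. The upper bound on unprompted time is 59 × 15 = 885 subject-days, or 885 / 365.25 = 2.4 subject-years. For IS1 subjects the interval can extend to day 5 + 15 = 20 after implant.

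**Step 3. Can the stated endpoint still be answered?** The endpoint is absence of USADE during the automatic tests.

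- All AEs in that window are reportable (10.2, 6.1.2, 6.1.3).
- A USADE is serious by definition, and relationship must be assessed for every reported SAE.
- The feature is available only while the device is interrogated by the clinical programmer (5.3).

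So the endpoint can be answered from the planned data.

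**Step 4. Causality for non-serious AEs.** An ADE is defined in the glossary by relatedness. The only explicit instruction in 10.2 to assess relationship covers SAEs, while SAP 14.1 and 14.2 code relationship for AEs in general and count unknown as related. Section 10.2 also asks for all information that the AE eCRF needs, but the eCRF is not among the documents. What is missing is an instruction; missing data are not shown.

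**The case against.** The strongest reply is that the plan is restricted on purpose and says so. The investigation concerns a software function in CE-marked devices that are already implanted, and the function acts only under the programmer. SAP 14.1 lists the restricted scope just before the 14.2 tables. The endpoint wording speaks of SAEs collected at each follow-up or visit, which is not a promise to collect every SAE. The duty in 10.2 is continuous from consent, with a 3-day limit, so a missing checklist line cancels nothing. Protocol 10.2 makes the investigator responsible for informing the ethics committee under local rules, and 10.3 defers to the committee's own guidelines, so committee reporting need not pass through the study database.

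Much of this stands. A restricted scope is a legitimate choice, and the general duty does cover inclusion to M0. What remains is that 10.3 and 4.1.3 e state no restriction, the 14.2 rows carry no scope label, and a duty that starts with awareness works better when a visit asks the question.

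A reader might infer more than this, and the documents do not support it:

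- That absence of USADE cannot be judged. Step 3 shows that it can.
- That only serious cardiovascular and access-site events are collected outside testing. Deaths, USADEs and device deficiencies are collected too.
- That the safety endpoint rests on the ADE count. That count is a descriptive row in SAP 14.2.
- That causality is missing for non-serious AEs. Without the eCRF this is not shown.

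**Conclusion.** The inconsistency is real and should be corrected, but its reach is limited. Outside testing, non-fatal SAEs beyond the 10.2 list (including anticipated SADEs) and non-serious ADEs need not reach the sponsor unless they come in with a device deficiency. The SAP 14.2 rows for AEs, ADEs, SAEs and expected SADEs are therefore not whole-study totals. Separately, up to 15 days per subject between inclusion and M0 are covered by a general duty but by no scheduled question.

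The number of events affected cannot be derived, because the documents give no event rate for this population. The 885 subject-days are a ceiling that puts every subject at the end of the M0 window.

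The conclusion that the USADE endpoint stays answerable assumes that testing at both M0 and M1 falls under the all-AE rule. The text of 10.2 and both visit lists say so, although the 10.2 timeline table and SAP 14.1 refer to the initial testing procedure.

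**What to change.** 1. **M0 prompt.** Add to protocol 6.1.2 and to the M0 row of the synopsis an item to report the serious events listed in 10.2 that have occurred since inclusion. Cost: one line and one question at a visit already planned.
2. **Reconcile 10.2 with 10.3 and 4.1.3 e**, in one of two ways:
   - Collect all SAEs from consent to termination. Cost: a few more AE eCRF pages in 59 subjects followed for about 3 months. Non-serious AEs outside testing would still be uncollected, so the rows for any AEs and any ADEs would still need a scope label.
   - Keep the restricted scope, state it in 10.3 and 4.1.3 e, and label the SAP 11.1 A and 14.2 outputs with it. Cost: wording only. This also works if collection has already ended, which is possible because SAP 17.8 names an M0 and M1 data extract whose file name ends in 20180112.
3. **Causality.** State in protocol 10.2 that relationship to device and procedure is recorded for every reported AE, as SAP 14.1 and 14.2 assume. Cost: one sentence, if the eCRF already holds the field.

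The same edit can add access-site events to the M1 item and align the references to initial testing with testing at both visits.

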10.3. SPONSOR REPORTING RESPONSIBILITIES

The Sponsor is responsible for reporting serious adverse event information to all participating investigators, ECs and regulatory authorities, as applicable following local regulations. USADE investigation results will be reported to the competent authorities all ECs and all participating investigators within 10 working days of the Sponsor's first notice of the effect. The Sponsor will also notify the competent authorities, all ECs, and all participating investigators of any EC withdrawal of approval within 5 working days of receipt of the approval withdrawal.

If the Sponsor determines an USADE to be an unreasonable risk to subjects, all parts of the investigation presenting that risk will be terminated or suspended as soon as possible, no later than 5 working days after said termination and no later than 15 working days after the Sponsor' first notice of the USADE. All SAEs must be reported to EC following the EC's safety reporting guidelines. The suspended study may not resume until the study has received both EC and FDA approval.

10.4. CONTACT DETAILS FOR REPORTING SERIOUS ADVERSE EVENTS AND SERIOUS ADVERSE DEVICE EFFECTS

In case of questions for reporting of adverse events, please contact the Clinical Project Manager of the study or the Monitor responsible for your site.

11. INDEPENDENT CLINICAL STUDY COMMITTEES: INDEPENDENT REVIEWER

An independent physician will review and adjudicate technical data of the LV pacing threshold value provided by the algorithm.

12. ADMINISTRATIVE REQUIREMENTS

12.1. ETHICS COMMITTEE (EC)

Subject inclusion cannot start before written approval of Ethics Committee (EC) of the CIP and the informed consent.

The Principal Investigator must report to the Sponsor withdrawal of EC approval within 5 working days. This study will be managed in accordance and full compliance with recognized Good Clinical Practices (ISO14155).

12.2. INFORMED CONSENT PROCESS

The investigational site must obtain written informed consent from each subject before any study procedures or evaluations are obtained. The informed consent form must be approved by the Sponsor prior to EC submission and by the EC prior to subject enrollment.

Subject information and consent contain all relevant aspects pertaining to the clinical investigation in writing and in native, non-technical and understandable language.

Subject's informed consent must be obtained and documented according to the principles of informed consent in the current version of the Declaration of Helsinki for Protection of Human Subjects, ISO 14155, and any local regulations, as applicable.

Failure to obtain subject consent needs to be reported to the applicable regulatory authority according to their requirements by either the site or the Sponsor.

Process for obtaining informed consent

Prior to inclusion, information should be given in a language and at a level of complexity understandable to the subject in both oral and written form by the Investigator or designee. Subjects should not be coerced, persuaded, or unduly influenced to participate or continue to participate in the study. Subject must be given ample time and opportunity to inquire about details of the study and all questions about the study should be answered to the satisfaction of the subject.

Prior to inclusion, where applicable per local regulation, the written informed consent form should be signed and personally dated by the subject, and by the person who conducted the informed consent discussion (Investigator or designee). If the subject is unable to read the consent form, a witness should be present during the entire informed consent discussion. After the informed consent is read to the subject and signed by the subject, the witness should also sign the consent form, attesting the subject freely gave that informed consent.

The subject must receive a copy of the signed and dated informed consent.

The consent form that is to be used must be approved by both the reviewing Ethics Committee and by the Sponsor.

Any violations of the informed consent process must be reported as deviations to the sponsor and local regulatory authorities, as appropriate.

